## **7.4 Statistical methods and determination of sample size**

### **7.4.1 Statistical evaluation**

Details of the statistical methods are provided in the following section. Any additional information will be documented in a comprehensive Statistical Analysis Plan (SAP), which will be prepared and finalised prior to database lock. All statistical analyses will be carried out under the direction the Biostatistics Group, AstraZeneca.

### **7.4.2 Description of variables in relation to hypotheses**

The primary objective is to determine the safety and tolerability of twice-daily dosing of AZD2281 when administered in combination with cisplatin to patients with advanced solid tumours. This objective will be assessed by adverse events, vital signs (blood pressure and pulse rate), haematology, clinical chemistry, urinalysis and physical examination. The safety data will also be used to establish the desired dose or MTD of the combination therapy and identify the DLT of the combination of AZD2281 and cisplatin.

The secondary objective of comparing exposure to AZD2281 when given alone and in combination with cisplatin will be assessed using PK parameters  $C_{max}$ ,  $t_{max}$ ,  $AUC_{0-t}$ .

A secondary objective is to make an assessment of the anti-tumour activity of AZD2281 in combination with cisplatin and versus cisplatin alone. This will be made using ORR and summaries of Best Overall Response (CR, PR, SD or PD).

### **7.4.3 Description of analysis sets**

When assessing safety and tolerability, summaries will be produced based on the Safety Analysis Set. This is a subset of the Full Analysis Set (FAS) which includes all patients who received at least one dose of study medication. Treatment group summaries will be according to initial dose of study treatment actually received.

If a patient discontinues study medication and starts another anti-cancer therapy, all subsequent safety data for that patient after 30 days from discontinuation will be excluded from the assessment of safety.

Only PK-evaluable patients will be included in the analysis of PK parameters. Such patients are those with sufficient PK data available with no protocol violations or deviations likely to have a significant impact on the PK parameters.

A strategy for dealing with data affected by protocol violations or deviations will be agreed by the investigator, study team physician and statistician before any formal data summaries are produced.

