#### **4.2.3 AZD2281 Monotherapy**

Upon completion of cycle 6 (ie, 21 days after last dose of chemotherapy), cisplatin may be discontinued and AZD2281 alone may be continued at the optimal monotherapy dose (i.e. 400 mg bid) at the investigators discretion.

The first dose of olaparib maintenance (Day 1 of olaparib maintenance phase) is the day after the chemotherapy discontinuation visit.

Following the patients' first dose of olaparib maintenance, they will return to the clinic for safety assessments at days 8, 15, 22 and 43, and then every 6 weeks thereafter relative to monotherapy day1 until objective disease progression as per RECIST criteria (assessed every 12 weeks), unless any other discontinuation criteria are met. See [Table 5](#) for specific assessments and time points.

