#### 4.5.2.2 Cisplatin

Cisplatin should be prepared in accordance with the local prescribing guidelines. Cisplatin will be administered 2 hours (+/- 1 hour) after the first (morning) dose of AZD2281 every 3 weeks.

- **Dose:** cisplatin 75 mg/m^2 IV q3 weeks or cisplatin 60 mg/m^2 IV q3 weeks
- **Infusion Time:** 60 minutes.
- **Anti-Emetic Premedication.** Patients should receive prophylactic anti-nausea medications such as ondansetron 24 mg po/iv x 1, dexamethasone 10 mg –20 mg po/iv x 1, prochlorperazine 10 mg po x 1 prn, and/or lorazepam 1 mg iv/po x 1 prn prior to cisplatin therapy.
- **Pretreatment Hydration:** Hydration may be achieved by IV infusion of 1 litre of sodium chloride 0.9% over 1-2 hours prior to cisplatin infusion
- **Treatment:** Give 12.5 gm iv of mannitol 20% or mannitol 25% 30 minutes prior to cisplatin infusion. Mix cisplatin in 100-500 ml sodium chloride 0.9% and infuse IV over 60 minutes. Ensure there is adequate urine output averaging at least 100cc/hr prior to cisplatin infusion
- **Post treatment Hydration:** Patient should receive 1 litre of sodium chloride 0.9% iv over 1-2 hours after cisplatin administration.

In this phase I study, after patients have completed 4 cycles of cisplatin based therapy at the full dose of 75 mg/m^2, or a dose of 60 mg/m^2 for those patients that received the lower cisplatin dosing treatment cohort option, subsequent cycles of cisplatin may be administered at a reduced dose as low as and including 50 mg/m^2 at the investigator's discretion as long as the patient is continuing to derive clinical benefit and has not met the criteria for progressive disease or any other discontinuation criteria. (see section [4.4.6.1](#))

In this study, after patients complete 6 cycles of cisplatin based therapy, cisplatin may be discontinued and AZD2281 may be continued at the optimal monotherapy dose (i.e., 400 mg bid) at the investigators discretion, as long as the patient is continuing to derive clinical benefit and has not met the criteria for progressive disease or any other discontinuation criteria. See [Table 5](#)

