### **6.6.1 Patient Management Post Data cut-off**

#### **6.6.1.1 Patients continuing on AZD2281**

[figure not shown]
There will be a final data cut-off defined as the time when all patients receiving AZD2281 have been followed for a minimum of 3 months of monotherapy AZD2281 following combination treatment, or there are no more patients remaining on treatment in the study; whichever is the earlier date. At this time point, the clinical study database will close to new data. Patients are however permitted to continue to receive study treatment beyond the closure of the database if, in the opinion of the investigator, they are continuing to receive benefit from treatment with AZD2281. Patients continuing on study treatment will be followed for core safety assessments only (haematology, clinical chemistry, AEs/SAEs and concomitant medications, IMP dosing details).

For patients who do continue to receive treatment beyond the time of this data cut-off, investigators will continue to report all SAEs to AstraZeneca Patient Safety until 30 days after study treatment is discontinued, in accordance with Section 5.10.4 (Reporting of Serious Adverse Events). Additionally as stated in Section 5.10.3 (Recording of adverse events), any SAE or non-serious adverse event that is ongoing at the time of this data cut-off, must be followed up to resolution unless the event is considered by the investigator to be unlikely to resolve, or the patient is lost to follow-up.

Patients continuing on monotherapy AZD2281 at the data cut-off should attend visits according to routine clinical practice but at least every 8 weeks until they meet any discontinuation criteria as per Section 4.4.6.1.

Drug accountability should continue to be performed until the patient stops study treatment completely.

**Figure 4** Flowchart to describe how to handle patients after the data cut-off date

\* Core safety assessments - haematology, clinical chemistry, AEs, concomitant medications

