### **7.2 Efficacy evaluation**

#### **7.2.1 Calculation or derivation of efficacy variables**

ORR is defined as the percentage of patients who have at least one RECIST assessment response of CR or PR. Data obtained up until progression, or last evaluable assessment in the absence of progression will be included in the assessment of ORR. The ORR will be based on the investigator visit assessment of RECIST response and will not be derived programmatically by AZ. Depending on the number of patients with non-measurable disease, ORR may also be calculated for the subset of patients with measurable disease only

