#### **7.4.4 Methods of statistical analyses**

No formal statistical analyses will be performed on safety data (primary objective), PK data, and efficacy data. All data will be summarised descriptively and where appropriate, confidence intervals will be presented as measures of study precision

Categorisation of response rate will be based on the RECIST criteria ([Therasse et al 2000](#)) using the following response categories: complete response (CR), partial response (PR), stable disease (SD) and progressive disease (PD). A patient will be classified as a responder if the RECIST criteria for a CR or PR are satisfied at any time up to and including the defined analysis cut-off point. ORR is the number of CR and PR divided by the number of enrolled patients evaluable for RECIST.

ORR will be analysed in the same way as described for the primary analysis. ORR and best overall objective response categories will be summarised at each assessment and overall by allocated study treatment. Conformed responses will be summarised where possible. The proportion of patients with responses will be presented along with corresponding 95% confidence intervals using the Wilson score method ([Newcombe 1998](#)).

Safety, tolerability and PK data will be summarised descriptively and with plots, further details of which will be provided in the SAP.

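### Overall safety summaries and ORR are not split at the switch to AZD2281 monotherapy, so monotherapy events and first responses can be credited to the starting combination cohort

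*Protocol*

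**What the plan says.** **Grouping of safety data.** Protocol Section 7.4.3: "Treatment group summaries will be according to initial dose of study treatment actually received". The only time limit it sets on safety data applies to patients who stop study medication and start another anti-cancer therapy; their data more than 30 days after discontinuation are dropped. Continuing on AZD2281 alone does not trigger it.

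**Response.** Section 7.2.1: "Data obtained up until progression, or last evaluable assessment in the absence of progression will be included in the assessment of ORR". Section 7.4.4 calls a patient a responder if the criteria for CR or PR "are satisfied at any time up to and including the defined analysis cut-off point", and adds: "ORR and best overall objective response categories will be summarised at each assessment and overall by allocated study treatment".

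**The switch.** Section 4.2.3 provides that, on completing cycle 6, "cisplatin may be discontinued and AZD2281 alone may be continued at the optimal monotherapy dose (i.e. 400 mg bid) at the investigators discretion". Section 4.5.2.2 repeats this. Sections 4.1.1 and 4.4.6.1 allow AZD2281 alone, with escalation to 400 mg bid, once cisplatin is permanently stopped for cisplatin toxicity, and Table 8 does so for grade 4 non-haematologic cisplatin toxicity. These routes can come before cycle 6.

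**Cut-off.** Under Section 6.6.1.1 the database closes when all patients receiving AZD2281 have been "followed for a minimum of 3 months of monotherapy AZD2281 following combination treatment", or when no patient remains on treatment, whichever is earlier. Table 5 schedules adverse event collection and tumour scans during monotherapy.

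**The concern.** The primary objective (Section 3.1) is the tolerability of AZD2281 given with cisplatin. The response objective (Section 3.2) is the activity of that combination. The protocol treats monotherapy as a distinct phase in its conduct: it has its own visit schedule (Table 5), its own toxicity rules (Section 4.5.3.9), and Section 4.1.1 limits the bar on intra-patient escalation to combination treatment. The analysis section does not carry this boundary over.

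A grade 3 event or a first partial response on AZD2281 alone at 400 mg bid would then be tabulated under, for example, 50 mg bid on days 1-5 with cisplatin. How much of this mixing occurs in each cohort depends on how many patients switch and when, which is partly at the investigator's discretion. With cohorts of about 3 to 12 patients, one or two such events can change the apparent pattern across dose levels.

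**Working it through.** The protocol states no figure for this point, so there is none to reproduce. The check is whether any section separates the phases, followed by illustrations of size.

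**1. Is there a boundary anywhere?** Section 7.4.3 fixes the grouping by first dose. Section 7.2.1 ends the response data at progression or the last evaluable assessment. Section 7.4.4 ends them at the cut-off. None of them refers to the stop of cisplatin or the start of monotherapy.

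**2. Follow-up off the combination.**
- Six cycles: 6 × 21 = 126 days = 18 weeks. Minimum monotherapy: 3 months, taken as 12 weeks.
- Share off the combination: 12 / (18 + 12) = 12/30 = 40%.
- If cisplatin stops after two cycles (6 weeks): 12 / (6 + 12) = 12/18 = 67%.

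These shares apply to a patient who switches and stays at least 12 weeks.

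**3. Do scans fall in the monotherapy phase before cut-off?** Table 5 places scans at weeks 9 and 18, then every 12 weeks from cycle 1 day 1. After a week-18 switch the next scan is at 18 + 12 = week 30, which is 12 weeks into monotherapy. A first response can therefore be recorded on monotherapy before the cut-off.

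**4. Effect of one such response.** Wilson 95% interval, as named in Section 7.4.4: [p + z²/2n ± z√(p(1−p)/n + z²/4n²)] / (1 + z²/n), with z = 1.96.

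| Cohort size | Without it | With it |
|---|---|---|
| 6 | 1/6 = 16.7% (3.0 to 56.4%) | 2/6 = 33.3% (9.7 to 70.0%) |
| 12 | 1/12 = 8.3% (1.5 to 35.4%) | 2/12 = 16.7% (4.7 to 44.8%) |

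**5. Effect on safety tables.** Assume that all 6 patients in a cohort switch and that each has probability p of a related grade 3 or higher event on monotherapy. The chance that at least one is credited to the starting dose is 1 − (1 − p)⁶:
- p = 0.10: 47%
- p = 0.246: 82%
- p = 0.35: 92%

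The middle value is the 24.6% (14 of 57) in Section 2 for the Phase II ovarian study, pooled over 100 and 400 mg bid. The other two are assumed. The true rate here, and the number who switch, are unknown.

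**6. Contrast in AZD2281 amount per 21 days.**
- 400 mg bid continuous: 400 × 2 × 21 = 16,800 mg.
- 50 mg bid continuous: 50 × 2 × 21 = 2,100 mg (16,800 is 8 times this).
- 100 mg bid days 1-10: 100 × 2 × 10 = 2,000 mg (8.4 times).
- 50 mg bid days 1-5: 50 × 2 × 5 = 500 mg (33.6 times).

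This shows only that the regimens differ. It does not measure bias, because cisplatin has stopped and milligrams are not event rates.

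**7. Where the response cut should fall.** With no delays and cycle 1 day 1 as day 1, the sixth cisplatin dose is on day 106. The chemotherapy discontinuation visit, 21 days later, is day 127, and monotherapy Day 1 is day 128 (Section 4.2.3). The week-18 scan is due on day 127 ± 7, that is days 120 to 134. An in-window scan can thus fall 134 − 128 = 6 days after monotherapy Day 1 and still reflect six combination cycles. A cut strictly before monotherapy Day 1 would wrongly remove it.

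**The case against.** **Much of the safety detail belongs to the SAP.** Section 7.4.4 leaves further safety detail to the SAP, which is not at hand. Columns by initial dose are compatible with separate tables by phase, so the SAP may already split them. This stands in part: it lowers the weight of the safety half. But the protocol fixes the grouping rule without limiting it to a phase, and fixes the open response window itself.

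**Dose decisions are untouched.** A reader might infer that the grouping distorts the MTD or fails the study's objectives altogether. The documents do not support that. DLT is confined to cycle 1 (Section 4.1.2), the MTD follows from DLT (Section 4.1.3), and cohorts are reviewed after 21 days (Sections 7.5 and 7.6).

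**Response timing is partly visible.** Response is grouped by allocated treatment and also shown at each assessment, so late responses can be seen by scan. This helps only partly. Some patients switch before cycle 6 and others may stay on the combination beyond it, so one scan can mix both regimens.

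**Best response up to progression is the protocol's RECIST rule.** Appendix D, Section 4.6, takes the best response from start of treatment to progression. That is a reason to keep an any-time ORR, but as a supportive figure. A reader might also infer that ORR will be inflated. That is possible but not shown, since many responses may come before the switch.

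**The cut-off may come without 3 months of monotherapy** if no patient remains on treatment. That is so, but monotherapy data already collected would still be in the database.

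**Conclusion.** The point holds for the overall safety summaries and for ORR. As the rules stand, events and first responses arising on AZD2281 alone can be reported under the starting combination cohort, and nothing in the protocol separates them. It does not reach the cycle-1 DLT assessment or the MTD.

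The size cannot be fixed in advance, because the switch is optional and the number who make it is unknown. The 40% share of follow-up, the move from 16.7% to 33.3% in a cohort of 6, and the 47% to 92% chance of at least one misattributed event are illustrations under the assumptions given with them. The wide Wilson intervals show that ORR is imprecise with or without the split; the issue is which regimen the figure describes.

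This should be fixed. It is not critical, because all analyses are descriptive and the needed dates are collected.

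**What to change.** **Section 7.4.3.** State that initial-dose grouping applies to the combination phase: from the first combination dose to the day before the first monotherapy dose, or to the last dose plus 30 days if there is no monotherapy. Report the monotherapy phase under its own heading. Give a whole-study total as supportive, so that late cisplatin effects stay visible; Section 4.5.3.8 notes that neuropathy may begin 3 to 8 weeks after the last cisplatin dose.

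**Sections 7.2.1 and 7.4.4.** Count a response towards combination ORR if it is first documented on a scan up to and including the scheduled end-of-combination scan within its ±1 week window, even if that scan falls a few days after monotherapy Day 1. State how this applies to patients whose cisplatin stops before cycle 6. List responses first seen later separately, and keep the any-time ORR as supportive.

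**Cost.** Analysis wording and extra tables. Monotherapy Day 1 is a scheduled visit and dosing is recorded in the CRF, so no new data and no change to patient management are needed. The small downside is that some late cisplatin effects will appear in the monotherapy table, which the whole-study total offsets.

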#### **7.4.4 Methods of statistical analyses**

No formal statistical analyses will be performed on safety data (primary objective), PK data, and efficacy data. All data will be summarised descriptively and where appropriate, confidence intervals will be presented as measures of study precision

Categorisation of response rate will be based on the RECIST criteria ([Therasse et al 2000](#)) using the following response categories: complete response (CR), partial response (PR), stable disease (SD) and progressive disease (PD). A patient will be classified as a responder if the RECIST criteria for a CR or PR are satisfied at any time up to and including the defined analysis cut-off point. ORR is the number of CR and PR divided by the number of enrolled patients evaluable for RECIST.

ORR will be analysed in the same way as described for the primary analysis. ORR and best overall objective response categories will be summarised at each assessment and overall by allocated study treatment. Conformed responses will be summarised where possible. The proportion of patients with responses will be presented along with corresponding 95% confidence intervals using the Wilson score method ([Newcombe 1998](#)).

Safety, tolerability and PK data will be summarised descriptively and with plots, further details of which will be provided in the SAP.

#### **7.4.5 Determination of sample size**

The primary objective of the study is safety and tolerability of ascending doses of AZD2281 in combination with cisplatin. The total number of patients has, therefore, been based on the desire to obtain adequate safety and tolerability data whilst exposing as few patients as possible to the study treatment and procedures. A patient will be defined as evaluable for safety review if they complete at least 1 cycle of cisplatin (3 weeks) and also receive at least 75% of either continuous or intermittent daily treatment of AZD2281 or they experience a DLT prior to completing 21 days of either continuous or intermittent treatment. If there are fewer than 3 evaluable patients in a given cohort then further patients will be recruited to the cohort until there are at least 3 evaluable patients. Once the dose or MTD has been determined (or the highest dose level has been explored) the cohort will be expanded to ensure that there are 6 evaluable patients who have completed four cycles of treatment.

### **7.5 Interim analyses**

Safety, tolerability and PK data (if decided needed) from each cohort will be reviewed on an ongoing basis by the safety monitoring committee (see Section [7.6](#)).

At least 3 evaluable patients in a given cohort must be treated, followed up and assessed for 21 days prior to recruiting patients into subsequent cohorts. In addition, the first patient in

each cohort will have to provide acceptable Day 7 safety data before further patients can be included.

## **7.6 Data monitoring committee**

Once all evaluable patients within a dose cohort have completed 21 days treatment, a safety monitoring committee comprising the Investigator, the Study Team Physician, the Safety Physician, the study team pharmacokineticist (if needed) and the Study Team Statistician (or nominated deputy in each case) will meet to assess the safety and tolerability data. The committee must comprise of a minimum of 3 physicians but may also include other members of the study team and an independent physician. Escalation to the next dose cohort will only occur if the committee consider that the maximum well-tolerated dose has not yet been defined.

All dose escalation and scheduling decisions will be the responsibility of the safety monitoring committee. No formal statistical analysis will be performed in the safety reviews.

## **8. ETHICS**

### **8.1 Ethics review**

An Ethics Committee should approve the final study protocol, including the final version of the Informed Consent Form(s) including biomarker and /or pharmacogenetic sample consents and any other written information and/or materials to be provided to the patients.

The investigator will ensure the distribution of these documents to the applicable Ethics Committee, and to the study site staff.

The opinion of the Ethics Committee should be given in writing. The investigator should submit the written approval to AstraZeneca before enrolment of any patient into the study.

The Ethics Committee should approve all advertising used to recruit patients for the study.

AstraZeneca should approve any modifications to the Informed Consent Form that are needed to meet local requirements.

If required by local regulations, the protocol should be re-approved by the Ethics Committee annually.

Before enrolment of any patient into the study, the final study protocol, including the final version of the Informed Consent Form, is approved by the national regulatory authority or a notification to the national regulatory authority is done, according to local regulations.

AstraZeneca will handle the distribution of any of these documents to the national regulatory authorities.

AstraZeneca will provide Regulatory Authorities, Ethics Committees and Principal Investigators with safety updates/reports according to local requirements, including SUSARs (Suspected Unexpected Serious Adverse Reactions), where relevant.

Each Principal investigator is responsible for providing the Ethics Committees/IRB with reports of any serious and unexpected adverse drug reactions from any other study conducted with the investigational product. AstraZeneca will provide this information to the Principal investigator so that he/she can meet these reporting requirements.

Where there is a genetic research, approval must be obtained for this genetic research and the associated genetic informed consent from the Ethics Committee. It must be clearly stated in the approval that this genetic research is approved. The investigator must submit written approval to AstraZeneca before any patient participates in this genetic research.

